### 10.11. Hirsutism and Acne

Visual analog scales (VAS) were used to assess the subject's perception of severity of hirsutism (female subjects only) and acne (all subjects), scored on a 100 mm visual analog scale from 0 mm (no symptoms) to 100 mm (very severe symptoms). Observed and change from OL baseline values in VAS scores for hirsutism and acne will be summarized descriptively by visit and treatment group. Summaries of acne VAS scores will be presented by sex as well as both sexes combined.

The above summaries will be repeated for the change from baseline to Week 52 in VAS scores for hirsutism and acne.

# **11. SAFETY**

The safety objective of the study is to characterize the safety and tolerability profile of crinecerfont as measured by TEAEs (including SAEs), clinical laboratory tests, vital signs, ECG, and neuropsychiatric assessments. All outputs for safety endpoints will be based on the DB Period Safety Analysis Set during the DB period and on the OL Period Safety Analysis Set during the DB period and on the OL Period Safety Analysis Set during the be summarized descriptively by treatment group. Safety data will not be subject to any imputation and will be summarized on an observed-case basis. No formal hypothesis-testing analysis of safety data will be performed. Unless otherwise noted, the below summaries will be produced for the DB period and the OL period separately and will follow the treatment-period specific treatment group and baseline definitions (as described in Section 6). All by-visit safety tables will also include a safety follow-up visit summary (as defined in Table 5) and subject data collected after the safety follow-up visit will not be summarized.

# 11.1. Study Drug Dosing and Compliance

The duration of exposure to crinecerfont will be calculated as: last dose date – first dose date +1.

Duration of exposure to crinecerfont will be summarized with descriptive statistics over the DB and OL periods (ie, table will include cumulative exposure from both treatment periods). The number and percentage of subjects with the following exposure categories will also be presented:

- > 0 to < 4 weeks
- $\geq$  4 weeks to < 16 weeks
- $\geq 16$  weeks to < 28 weeks
- $\geq 28$  weeks to < 40 weeks
- $\geq$  40 weeks to < 52 weeks
- $\geq 52$  weeks

At each visit where study drug is dispensed, the site will enter the kit number(s) dispensed and returned as well as the total number of capsules dispensed and returned for the kits combined. The subject's compliance will be calculated at each visit (when kits are returned) as the total number of capsules dispensed – total capsules returned divided by the expected number of capsules taken by the subject during the visit interval. For subjects receiving the oral solution, compliance will be determined based on the weight of the dispensed and returned study drug. The number and percentage of subjects in each treatment group who are dosing compliant (defined as < 80%,  $\ge$  80% to  $\le$  120%, > 120%) will be presented for each postbaseline visit when study drug is returned. Compliance will be summarized separately for the DB and OL periods.

## 11.2. Adverse Events

A treatment-emergent adverse event (TEAE) is an AE not present prior to the initiation of study drug dosing, or is an already present event that worsens either in intensity or frequency following the initiation of study drug dosing with an onset on or before the last dose of study drug + 28 days (to account for the study drug washout period).

TEAEs will be further defined for the two treatment periods. For the DB period, Investigators will be asked to respond "Yes" or "No" on the eCRF as to whether the AE started after the subject took the first dose of study drug. An AE with a response of "Yes" and that occurs on or before the last dose of study drug in the DB period will be classified as a TEAE for the DB period. If the subject's last dose on study occurs in the DB period, then any AE occurring prior to or on the last dose of study drug in the DB period + 28 days will be considered a TEAE. If the investigator's response is missing, then the treatment emergent status will be derived based on the AE onset date relative to the date of the subject's first dose of study drug in the DB period or first dose of study drug in the OL period. If the AE onset date is unknown, it will be assumed that the AE is a TEAE and will be reported in the DB period TEAE summaries.

For the OL period, TEAEs will be defined as AEs starting after the first dose of study drug in the OL period and prior to the last dose of study drug in the OL period. If the subject's last dose on study occurs in the OL period, then any AE occurring prior to or on the last dose of study drug in the OL period + 28 days will be considered a TEAE.

TEAEs that are ongoing at the time of a datacut will be summarized once according to the treatment period in which the TEAE started.

Adverse events with an onset date after the last dose of study drug + 28 days will not be considered treatment emergent (non-TEAEs).

The following TEAE summaries will be produced for the DB period (Day 1 up to Week 28) and for the 6-month OL period (Week 28 to Week 52) separately:

- TEAEs categorized by MedDRA system organ class (SOC) and/or preferred term (PT) will be summarized in frequency tables. The frequency tables will include the number and percentage of unique subjects experiencing each event one or more times by treatment group.
- Two similar frequency tables will be generated for TEAEs—one including both SOC and PT (sorted in alphabetical order), and one including PT only, with PTs sorted in order of decreasing frequency of subjects reporting the PT in the DB crinecerfont treatment group. Non-TEAEs will be summarized by SOC and PT only.
- An overall summary table will be provided that summarizes the number and percentage of unique subjects with any TEAE, any SAE, any TEAE leading to study drug discontinuation, any TEAE leading to study discontinuation, and any TEAE resulting in death. The summary table will also include the frequency distribution of the maximum TEAE intensity (mild, moderate, severe) reported for each subject.

The above summaries (TEAEs by SOC / PT, TEAEs by PT) will be generated for the following subgroups as well:

- age group (2 < 12 years; 12 17 years)
- Tanner stage (Tanner stage 1, 2; Tanner stages 3-5).

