Subjects will be randomized on Day 1 in a 2:1 ratio (active:placebo). Randomization will be stratified by pubertal stage (Tanner breast or genital stage 1 or 2 versus 3, 4, or 5) and sex. From the evening of the Day 1 visit (after all Day 1 assessments have been performed) until the morning of the Week 28 visit, all subjects will receive blinded study drug based on their Day 1 weight (25 mg bid via oral solution for subjects 10 to <20 kg, 50 mg bid via oral solution for subjects 20 to <55 kg, or 100 mg bid via oral capsules for subjects ≥55 kg). Study drug will be administered bid with the subject's breakfast and evening meals (each dose separated by approximately 12 hours).

From Day 1 until Week 4, subjects should maintain a stable glucocorticoid regimen to the extent possible, except for stress dosing if needed for illness or other significant physical stress, in order to assess the direct effect of study drug on adrenal androgens and precursors. Stress dosing of glucocorticoid (at any time during the study) can be based on guidance provided by the investigator, the subject's treating physician, or guidelines provided in the protocol (Appendix A).

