# 7.3. Open-Label Treatment Period (Week 28 to Week 52)

From the evening of the Week 28 visit (after all Week 28 assessments have been performed) until the morning of the Week 52 visit, all subjects will receive active study drug based on their Week 28 weight (crinecerfont; 25 mg bid via oral solution for subjects 10 to <20 kg, 50 mg bid via oral solution for subjects 20 to <55 kg, or 100 mg bid via oral capsules for subjects ≥55 kg) with breakfast and evening meals. Subjects and investigators will remain blinded to subjects' randomized treatment group assignment during the entire study. From Week 28 until Week 32, subjects should maintain a stable glucocorticoid regimen to the extent possible, except for stress dosing if needed for illness or other significant physical stress. A blood sample will be collected at Week 32 (at home or the study site).

For subjects who are on >11 mg/m²/day glucocorticoid dose (in hydrocortisone dose equivalents adjusted for BSA [based on weight and height at Week 28]) at Week 32, further adjustments in glucocorticoid dose should be made following guidelines similar to that used during the placebo-controlled period with the goal to reach a target dose of 8 to 10 mg/m²/day in hydrocortisone dose equivalents adjusted for BSA at Week 52, while A4 is controlled. The calculation of glucocorticoid dose in hydrocortisone equivalents adjusted for BSA at Week 52 will be based on height and weight measurement at Week 52. BSA will be updated at Week 40 if height measurement is obtained at Week 40.

The first glucocorticoid dose adjustment step during this period (if done) should be guided by the serum A4 change at Week 32 (compared with Week 28), after the subject has been on open-label active study drug as well as stable glucocorticoid regimen (to the extent possible) for 4 weeks. A suggested guideline is provided in Table 5 but the exact amount adjusted may differ from this guideline based on practical issues considered in clinical practice related to available dosage strengths. The investigator should contact the subject/guardian once the Week 32 lab results are available in order to provide guidance on the amount of the first glucocorticoid dose adjustment (if needed) during the open-label treatment period.

Table 5: Guide for Glucocorticoid Dose Adjustment During the Open-Label Treatment Period

Percent Change from Week 28 in Serum Androstenedione	Androstenedione Level	Glucocorticoid Dose Adjustment

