## 11.2. Recording Adverse Events

For randomized subjects, each AE will be listed as a separate entry on an AE eCRF. Screen failure subjects will have AE information noted only in the source document. The investigator (or designee) will provide information on dates of onset and resolution, intensity, seriousness, frequency, action(s) taken, changes in study drug usage, relationship to study drug, and outcome.

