#### 6.8.1. Start Dates for Adverse Events

For the purpose of estimating the time of the event in relationship to study drug (ie, study day), missing and incomplete ("partial") dates for AEs will be imputed using the following algorithm. For start dates that are missing day and month: impute 1st January, unless the year is the same as the first dose of study drug, in which case the start date will be imputed to the date of first dose of study drug. For start dates that are missing day alone: impute to the 1st of the month unless the

month and year are the same as the first dose of study drug, in which case the start date will be imputed to the date of first dose of study drug. There will be no imputation for AE stop dates.

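### The SAP's double-blind and open-label adverse event windows do not join up at the Week 28 switch: depending on how they are read, switch-day events are misattributed or fall in neither table

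*SAP*

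**What the plan says.** SAP Section 11.2 sets period-specific rules on top of a general TEAE definition that reaches to 28 days after the last dose.

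- **DB period.** Of the events that the investigator marks as starting after the first study drug dose, one "that occurs on or before the last dose of study drug in the DB period will be classified as a TEAE for the DB period". The extension to 28 days after the last DB dose applies only when the child's last dose on study was in the DB period. If the investigator's answer is missing, onset date is compared with the first DB or first OL dose date.
- **OL period.** "AEs starting after the first dose of study drug in the OL period and prior to the last dose of study drug" in that period, with a 28-day extension only when the last dose on study was in the OL period.

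The dosing schedule is in Protocol Sections 7.2 and 7.3. From Day 1, and "until the morning of the Week 28 visit, all subjects will receive blinded study drug based on their Day 1 weight". Open-label crinecerfont is then given "From the evening of the Week 28 visit (after all Week 28 assessments have been performed) until the morning of the Week 52 visit". As planned, the last blinded and first open-label doses share a calendar date.

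Protocol Section 11.2 says that the investigator supplies "dates of onset and resolution" for each event and mentions no onset time. TEAE tables are produced separately for the two periods, and DB data are shown by randomized group (SAP Sections 6.1 and 11.2).

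**The concern.** A pair of period rules should give each on-treatment event exactly one home. Here the DB window closes at the last DB dose and the OL window opens after the first OL dose, and nothing governs what lies between. Nor does any rule separate same-date onsets before the evening dose from those after it. The investigator's before/after question concerns the first study drug dose and is described only for the DB period.

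For a child randomized to placebo, the Week 28 evening dose is the first exposure to crinecerfont. The DB tables are the only placebo-controlled safety comparison, and the same period split carries over to the tables of discontinuations, serious events, acute adrenal insufficiency and stress dosing (SAP Sections 11.2.1 to 11.2.4). An event after that first dose should not appear as a placebo event, and should not disappear from both sets of tables.

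**Working it through.** The plan states no figure to reproduce; the check applies the written rules to onsets around the switch.

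**Rules applied** to a child who continues into the OL period, with the investigator's answer Yes:

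- DB if onset ≤ last DB dose.
- OL if first OL dose < onset < last OL dose.
- The 28-day DB extension does not apply.

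Call the date of the Week 28 visit D. The illustration takes the morning dose at 08:00 and the evening dose at 18:00. The second time is an assumption, and only the order matters.

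| Last DB dose | First OL dose | Reading by onset date | Reading by clock time |
|---|---|---|---|
| D, morning | D, evening (as planned) | All of D is DB, including after the evening dose; D+1 is OL; nothing lost | Between the doses: neither; after the evening dose: OL |
| D, morning | D+1, evening | D is DB; all of D+1 is in neither; D+2 is OL | Between the doses: neither; then OL |
| D, morning | D+3, evening | D is DB; D+1 to D+3 (3 dates) are in neither; D+4 is OL | Between the doses: neither; then OL |
| D−1, evening (morning dose missed) | D, evening | All of D is in neither; D+1 is OL | Between the doses: neither; then OL |

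**Which rows can occur.** The first is the protocol's plan. Later starts are possible because Week 28 assessments may be spread over several days within the visit window, and open-label treatment waits until they are complete (Protocol Synopsis and Table 7, footnote a).

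**Which reading applies.** The protocol's recording of onset dates supports the date reading. So does SAP Table 4, whose Week 28 analysis window closes on the first OL dose date and so treats the switch day as a DB day. The SAP does not state it outright.

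**Far end of the OL period.** OL dosing runs to the morning of the Week 52 visit. For a child entering the extension, an onset on that date is not before the last OL dose by date. The 28-day extension does not apply because dosing continues, so the event is outside the OL table.

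**Size.**

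- Misattribution window under the date reading: one evening to midnight per placebo child, within one of about 196 DB days (SAP Table 4 target day for Week 28). 1/196 = 0.5% is therefore an upper limit on the share of DB time.
- Effect on a rate: 27 placebo children are planned, so one additional child with a given event adds 1/27 = 3.7 percentage points. This is a maximum per child, because tables count unique subjects and a child who already had that event in the DB period adds nothing.
- The documents give no adverse event rate for this population and period, so no expected number of affected events can be derived.

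**The case against.** The strongest reply is that the problem is narrow and mostly harmless. The period rules speak of doses, and the protocol does not say that dates are the only timing recorded. On a clock reading no crinecerfont event is credited to placebo. Safety is descriptive, and the listings of serious events and discontinuations show study day and treatment period. Events missing from both period tables still meet the general TEAE definition, and the exposure-adjusted rate in SAP Section 11.2.5 pools both periods. Absorption is described as relatively slow (Protocol Section 5.2), which gives no support to a cluster of reactions before midnight on the first evening. Extension data have a separate SAP, which may pick up events on the last OL dose date.

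Most of this stands as an argument about size. It does not rescue the rules: the clock reading removes the misattribution only by opening a gap between the doses. The pooled rate is also reported by group without saying how switch-day onsets are attributed.

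Four stronger inferences are tempting and not supported:

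- **That the rules both misattribute and lose events.** These are alternatives. With the planned same-day switch read by date, nothing is lost. With a later OL start read by date, first-evening events are lost and not credited to placebo.
- **That all first-night events count as placebo.** Onsets after midnight carry the next date and are OL under the planned schedule.
- **That every switch-date event is a bias in favour of the drug.** Events before the evening dose belong in DB. Background events also enter DB from the 54 crinecerfont children, so at equal per-child rates they create no difference between arms.
- **That partial dates should be sent to OL.** SAP Section 6.8.1 uses the first of the month when only the day is missing, with the first study dose as its only anchor, so switch-month events go to DB in both arms. Sending them to OL would also strip crinecerfont-arm events from the controlled comparison. That is a trade-off, not a clear correction.

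**Conclusion.** The point holds as a defect in the period definitions: under neither reading do the two windows account for all the time around the switch. Under the planned same-day schedule and the date reading, which the documents favour, the consequence is that a placebo child's event between the first crinecerfont dose and midnight is shown under placebo. Under a later OL start or clock times, it is omission from both period-specific tables. Separately, last-OL-dose-date events are left out of the OL table for children entering the extension; whether the extension SAP captures them cannot be known from these documents.

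The expected effect is small and cannot be quantified here. The only firm bound is the 3.7 points per additional placebo child for a given event, assuming all 27 planned children are in the DB safety set. Any expected count of misassigned events would need an assumed event rate that neither document supplies. The case for acting is that the correction is cheap and affects the only controlled safety tables.

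**What to change.** Amend SAP Section 11.2 so that the periods are contiguous, and state whether each boundary is a date or a time.

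- **DB TEAE, children who continue:** onset after the first DB dose and before the first OL dose.
- **OL TEAE:** onset on or after the first OL dose and before the first extension dose.
- **Children whose last dose on study falls in a period:** keep the existing limit of last dose plus 28 days.
- **Onset on the switch date:** assign by recorded onset time or by an eCRF item asking whether the event began before or after the first open-label dose. Default to OL when this is unknown.

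The cost is SAP wording, a revised period flag and, if used, one eCRF item; no efficacy analysis changes. The downside is that, under the default, some events that began before the evening dose on the switch date would move to OL in both arms. The rule for incomplete onset dates can stay as it is.

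### The SAP's open-label TEAE rule omits worsening, so an event that starts double-blind and worsens after Week 28, if kept as one record, is tabulated only in the double-blind period

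*SAP*

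**What the plan says.** SAP 11.2 opens with a general definition. A TEAE is an event that was absent before dosing, "or is an already present event that worsens either in intensity or frequency following the initiation of study drug dosing". The section then states that "TEAEs will be further defined for the two treatment periods", and these further rules decide which table an event enters.

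- **DB rule.** The investigator answers Yes or No on the eCRF "as to whether the AE started after the subject took the first dose of study drug". If the answer is missing, "the treatment emergent status will be derived based on the AE onset date".
- **OL rule.** "For the OL period, TEAEs will be defined as AEs starting after the first dose of study drug in the OL period", with an upper limit at the last OL dose, extended by 28 days if that is the last dose on study.
- **Data cuts.** "TEAEs that are ongoing at the time of a datacut will be summarized once according to the treatment period in which the TEAE started".
- **Intensity.** The overall summary, produced separately for each period, includes the "frequency distribution of the maximum TEAE intensity (mild, moderate, severe) reported for each subject".

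SAP 6.1 reports OL data as placebo/crinecerfont, crinecerfont/crinecerfont and all subjects combined. Under Protocol 7.3 everyone receives crinecerfont from the evening of the Week 28 visit.

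Protocol 11.1 gives an open-ended list of what counts as an adverse event. The list includes worsening of conditions present at study start. A persistent symptom that predates dosing is not an adverse event unless it progresses unexpectedly or becomes more severe after dosing. Protocol 11.2 requires a separate eCRF entry for each adverse event. It does not say whether the worsening of an ongoing event opens a new entry.

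**The concern.** The general definition has two limbs, new onset and worsening. The period rules carry forward only the first. At Week 28 this matters, because treatment changes for the placebo group while some of its adverse events may still be ongoing. A child whose event began on placebo and became worse on crinecerfont fits the idea of the worsening limb, yet no sentence places that worsening in the OL tables.

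At stake is the safety description of first crinecerfont exposure in the switchers. The same gap would carry into the other tables built by period from TEAEs: discontinuation (SAP 11.2.1), serious events (11.2.2) and events leading to stress dosing (11.2.4). The exposure-adjusted rate in 11.2.5 does not fill it, since follow-up for a term ends at its first occurrence and a later worsening is not registered.

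**Working it through.** The plan states no figure on this point, so the check applies the rules of SAP 11.2 literally to test cases.

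**Inputs.** Week 28 is Day 196 and Week 52 is Day 364 (target days, SAP Table 4). Assume DB dosing on Days 1 to 196, OL dosing on Days 196 to 364, and continuation into the extension. The DB rule needs a start after the first DB dose and no later than the last DB dose. The OL rule needs a start after the first OL dose.

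| Case | DB table | OL table |
|---|---|---|
| (a) Starts Day 100 on placebo, worsens Day 230 on crinecerfont, one record | Yes (placebo) | No |
| (b) As (a), but the worsening is entered as a new event dated Day 230 | The Day 100 record only | Yes (placebo/crinecerfont) |
| (c) Starts Day 100 on crinecerfont, worsens Day 230, one record | Yes (crinecerfont) | No |
| (d) Present on Day -10, worsens Day 50 or Day 230, one record with its original start date | No | No |

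Cases (a) and (b) are the same clinical course. The record-keeping convention alone decides whether the OL table shows it. Case (c) shows that the rule treats both OL groups alike. In case (d) the general definition gives a TEAE and the period rules give none. If the worsening is instead entered as an event of its own, as Protocol 11.1 allows, it has a start date after dosing and is counted.

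**Intensity.** Protocol 11.1.1 asks for one intensity category per event. If that is the worst grade reached, the grade reached on Day 230 in case (a) enters the DB placebo maximum-intensity row, and in case (c) the DB crinecerfont row.

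**Scale.** SAP 3.3 plans 54 crinecerfont and 27 placebo children. If all enter the OL period, each affected child is:

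- placebo/crinecerfont column: 1/27 = 3.7 percentage points (2/27 = 7.4; 3/27 = 11.1);
- crinecerfont/crinecerfont column: 1/54 = 1.9 percentage points;
- combined column: 1/81 = 1.2 percentage points.

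These are sizes per affected child and do not forecast how many there will be. Neither document gives the proportion with an event ongoing at Week 28 or the proportion of those that worsen.

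**The case against.** The strongest reply is that the loss depends on a convention that is not in these documents. If the eCRF completion guide tells sites to open a new record when an event worsens, case (b) applies and the present OL rule already captures it. That is fair, and it makes the consequence conditional. It does not remove the conflict in SAP 11.2: neither document requires or forbids a split record, and the written OL rule still lacks a limb that the definition has.

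Some stronger readings are tempting but not supported:

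- **That the rule favours crinecerfont overall.** For switchers, the misplacement does take worsening out of a crinecerfont column and leave it under placebo. But case (c) leaves worsening under DB crinecerfont, in a group planned at twice the size. The net effect on the DB comparison is undetermined.
- **That the DB rule loses every pre-dose event that worsens.** Protocol 11.1 largely covers these, and any residual loss affects both arms.
- **That the data-cut sentence forces the result for any ongoing event.** It covers only events ongoing at a cut, such as the Week 28 analysis, which also takes in available data to Week 52 (SAP 5.1). The OL rule gives the same result without it.
- **That affected children vanish from the OL safety summary.** A child with another OL event still counts in the row for any TEAE. The loss is for the particular term.

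It is also true that safety is descriptive, with no hypothesis tests (SAP 11), and that events leading to discontinuation and serious events are listed with study day. A careful reader of the listings could find those cases. Ordinary worsening that is neither serious nor a cause of stopping has no such backstop among the specified outputs.

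**Conclusion.** The point holds as an internal inconsistency with a conditional consequence. SAP 11.2 counts worsening in its definition and omits it from the OL rule that fills the tables. An event that begins in the DB period, is kept as one record and worsens after the first OL dose is tabulated only in the DB period. The event does not lose TEAE status, because study drug includes placebo. The fault is the period, and for switchers the treatment, to which the worsening is attributed. The intensity effect needs the further assumption that the record carries its worst grade.

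The number of affected children cannot be derived from the documents, and 3.7 percentage points per switcher assumes that all 27 planned placebo children enter the OL period. No efficacy conclusion depends on this. It should still be corrected, because the tables could otherwise contradict the SAP's own definition at the point where placebo children first receive the drug.

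**What to change.** In SAP 11.2:

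1. Define an OL TEAE as an adverse event that starts, or worsens in intensity or frequency, after the first OL dose, and date it at the worsening. Keep to intensity and frequency, the two criteria in the SAP's own definition.
2. Add the same worsening clause to the DB rule, for consistency, for events that started before the first dose.
3. Limit the data-cut sentence to events that have not worsened in the later period, so that it does not undo item 1.
4. Assign maximum intensity to the period in which that intensity was reached.

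Items 1 and 4 need a date and grade for the worsening. A new adverse event record at worsening supplies both. Where records were not split, a review of events ongoing at the first OL dose would identify the cases.

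The cost is a few sentences in the SAP, an eCRF instruction if none exists, and a small amount of data review. A few events will be counted in both periods, which a table footnote can state.
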